9.1 Extent of Exposure

An integrated pharmacokinetic–adherence measure (IPAM) will be applied to determine the degree of regimen adherence (see Section 7.6 Treatment Compliance) for more details. In addition, ganciclovir concentration from PK analysis will be reported.

9.2 Adverse Events

Analyses of AEs will be based on data from all subjects receiving at least one dose of study drug. As per protocol, safety data will be collected only through Study Day 70, i.e., four weeks after the last study dose.

AEs will be reported by treatment based on the relation to study drug, toxicity grade, and body system. When calculating the incidence of adverse events, or any sub-classification thereof by treatment, time period, severity, etc., each subject will only be counted once and any repetitions of adverse events will be ignored; the denominator will be the total number in each treatment group or overall sample size as appropriate.

9.3 Deaths, Serious Adverse Events and other Significant Adverse Events

Analyses of SAEs will be based on data from all subjects receiving at least one dose of study drug. As per protocol, safety data will be collected from Study Day 1 through four weeks following the last dose of study drug.

9.4 Pregnancies

Not applicable to this study.

9.5 Clinical Laboratory Evaluations

Chemistry and hematology laboratory evaluations will be reported. The summary statistics will be produced in accordance with section 7. Flags are defined as values outside of the site- and age-specific normal ranges. The reported upper and lower limits by the site will be used to determine if the reported laboratory value was outside of the reported limits which will translate to a flag for the particular laboratory values. The number and percent (relative to the total laboratory done for that parameter) of flags will be reported in summary tables for each of the laboratory parameters. Means and standard errors of critical safety laboratory parameters (ANC, hemoglobin, WBC, platelet, ALT, bilirubin, and creatinine) over time will be displayed in a figure. Mixed model with random intercept and time, therapy and time by therapy interaction term will be used to compare the safety parameter at each time point between the treatment groups.

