    - BSER or VRA (to assess neuro-otologic status) and OAEs (DPOAE or TEOAE) will be obtained. If the BSER and/or VRA is abnormal, then bone conduction will be obtained to distinguish between sensorineural hearing loss, conductive loss, or mixed loss. If the OAEs are abnormal, then acoustic immittance measures (tympanometry and acoustic

reflexes) will be obtained to better define the middle or inner ear abnormality (e.g., otitis media).

- Virology specimens for CMV viral load (see Section 8.2.2.1)
- Confirm that Study Day 1 safety labs allow for dosing of study medication (see Section 6.3); if so, begin study medication on Study Day 1
- Updated results of any etiological investigations for SNHL.

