4.1 General Study Design and Plan

[figure not shown]
(ICH E3;9)

The current study evaluates whether six weeks of antiviral therapy can stabilize hearing deterioration in older infants, toddlers, and young children who have developed CMV-associated hearing loss. This study is a Phase II, international, multi-center, double-blind, placebo-controlled evaluation of six weeks of valganciclovir treatment for children (up to 4 years of age) with virologically-confirmed congenital CMV infection and hearing loss.

Patients meeting inclusion/exclusion criteria will be offered enrollment into the trial. Randomization on the study occurs when the diagnosis of congenital CMV infection is confirmed, and the subject is then assigned to receive either 6 weeks of oral valganciclovir or 6 weeks of placebo. Study subjects will be stratified according to age at randomization (1 through 11 months, 12 through 23 months, 24 through 35 months, and ≥ 36 months) and CMV involvements (symptomatic and asymptomatic at birth) as a marker of disease severity. An independent Data and Safety Monitoring Board (DSMB) will oversee the conduct of the trial. During the course of their oversight, they may request to have access to unblinded data.

The target sample size is 54 subjects (27 in each arm). Up to 20% over-enrollment will be allowed to replace subjects who drop-out or who have inadequate audiology assessments. The primary endpoint will be change in total ear hearing assessments (improved + no change versus other) between baseline and 6 months. Secondary and tertiary endpoints will be assessments of other measures of hearing outcomes; detection of viruria, viremia, and CMV in saliva by PCR six weeks and six months after trial entry; the quantitative log reduction in viruria, viremia, and CMV viral load in saliva detected after six weeks of therapy; correlation of change in viral load with change in total ear and best ear hearing at six months; incidences of unanticipated medically attended visits and adverse events which lead to permanent discontinuation of valganciclovir therapy or have an unresolved outcome; and assessments of blood concentration of ganciclovir after administration of valganciclovir. Stopping rules will be employed in order to limit exposure of study subjects to a potentially unacceptable treatment.

Figure 1: Schematic of Study Design

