4.3 Inclusion–Exclusion Criteria and General Study Population

(ICH E3;9.3. ICH E9;2.2.1)

Male and female infants from 1 month through 3 years of age (up to 4th birthday) with sensorineural hearing loss will be eligible for enrollment. Following confirmation of inclusion/exclusion criteria and the signing of informed consent, the subject's Guthrie card will be retrieved and tested for CMV DNA by PCR unless there is a virologically confirmed diagnosis of congenital CMV infection made within the first 30 days of life. Inclusion criteria were selected to ensure the inclusion of those subjects with congenital CMV disease. Exclusion criteria were selected to limit confounders for safety and efficacy. Renal insufficiency was an exclusion criterion because the active moiety, GCV, is renally cleared and a neonate's renal system is not fully developed. The study population is consistent with those patients seen in clinical practice and who receive IV GCV as standard of care to treat symptomatic congenital CMV.

Inclusion Criteria

- Signed informed consent from parent(s) or legal guardian(s)
- Sensorineural hearing loss (≥ 21 dB in one or both ears, documented within 12 weeks prior to study entry)
- Children from 1 month through 3 years of age (up to the 4th birthday)
-

Exclusion Criteria

- Imminent demise
- Profound sensorineural hearing loss (> 90 dB) in both ears
- Patients receiving other antiviral agents or immune globulin
- Gastrointestinal abnormality which might preclude absorption of an oral medication (e.g., a history of necrotizing enterocolitis)
- Documented renal insufficiency, as noted by a creatinine clearance < 10 mL/min/1.73m² at time of study enrollment
- Breastfeeding from mother who is receiving ganciclovir, valganciclovir, foscarnet, cidofovir, or maribavir
- Infants known to be born to women who are HIV positive (but HIV testing is not required for study entry).
- Current receipt of other investigational drugs
- Previous receipt of ganciclovir or valganciclovir

- Known hypersensitivity to ganciclovir, valganciclovir, or components of the product
- Inability to attend follow-up hearing and clinical assessments
- Infants with Auditory neuropathy/dyssynchrony.
- Children with another known etiology for SNHL (e.g. connexin 26, syndrome or metabolic disorder associated with SNHL, inner ear malformation and widened vestibular aqueducts, meningitis). Exclusion of each of these conditions is not required for trial enrollment.

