|---|-----|---------------------------------|---|----------------------|----------------------|-----------------------------------|--|
| Table 11a: Changes over Time in Hematology Parameters | 11a | At least one dose of study drug | Hematology Parameters | Baseline-Month 6 | Therapy Group, Visit | N, Mean, SD, 10th pctl, 90th pctl | General linear mixed model with random intercept was fitted for each parameter. Each model contains therapy, time and therapy by time interaction. |
| Table 11b: Changes over Time in Chemistry Parameters | 11b | At least one dose of study drug | Chemistry Parameters | Baseline-Month 6 | Therapy Group, Visit | N, Mean, SD, 10th pctl, 90th pctl | General linear mixed model with random intercept was fitted for each parameter. Each model contains therapy, time and therapy by time interaction. |
| Table 12: Maximum Degree of Neutropenia (Lowest ANC) During Day 1-42 Period | 12 | At least one dose of study drug | ANC | Randomization-Day 42 | Therapy Group | n, % | NA |
| Table 13: Maximum Degree of Anemia (Lowest HGB) for 11-0069 Valganciclovir | 13 | At least one dose of study drug | HGB | Randomization-Day 70 | NA | n, % | NA |
| Table 14: Maximum Degree of Anemia (Lowest PLT) for 11-0069 Valganciclovir | 14 | At least one dose of study drug | PLT | Randomization-Day 70 | NA | n, % | NA |
| Table 15: Maximum Degree of ALT (Highest ALT) for 11-0069 Valganciclovir | 15 | At least one dose of study drug | ALT | Randomization-Day 70 | NA | n, % | NA |
| Table 16: Maximum Degree of Creatinine (Highest creatinine) for 11-0069 Valganciclovir | 16 | At least one dose of study drug | creatinine | Randomization-Day 70 | NA | n, % | NA |
| Table 17: Summary of Concomitant Medications by Treatment Group (Blinded Treatment Phase) | 17 | At least one dose of study drug | Treatment Group (Blinded Treatment Phase) | Baseline-Day 48 | Therapy Group, Visit | n, % | NA |
| Table 18a: Dose (mg/kg) of Valganciclovir or Placebo | 18a | At least one dose of study drug | Dose | Day 1, 14 28 | Therapy Group, Visit | N, Mean, SD, Median, Min, Max | Fisher's exact and Wilcoxon test |

| | | | | | | | |
|---|-----|---------------------------------|---------------------------------|----------------------|----------------------|-------------------------------|--|

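### The laboratory model spends the pre-dose Day 1 value as an outcome instead of using it as a baseline, which costs precision in the by-visit safety contrasts (minor)

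*SAP*

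**What the plan says.** SAP 9.5 specifies a mixed model with a random intercept, in which "time, therapy and time by therapy interaction term will be used to compare the safety parameter at each time point between the treatment groups". The list of tables in SAP 17 repeats this for Tables 11a (hematology) and 11b (chemistry): "Each model contains therapy, time and therapy by time interaction". The row for Table 11a reads "Hematology Parameters | Baseline-Month 6 | Therapy Group, Visit", so baseline is one of the modelled visits.

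The baseline laboratory value is a pre-treatment value. Protocol 7.2 tells sites to "Confirm that Study Day 1 safety labs allow for dosing of study medication" before study drug is started. The schedule in SAP 4.5 puts safety labs at Days 1, 14, 28, 42 and 70.

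Neither the Day 1 value nor age is a covariate in the laboratory model. The covariate adjustment in SAP 6.3 is written for the primary hearing outcome.

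**The concern.** Both arms have the same expected Day 1 value, because allocation is random and no drug has been given. A model that estimates a free Day 1 mean per arm ignores this. The comparison the SAP names is the arm difference at each visit, not the difference in change. That contrast makes no use of where each child started.

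Safety and tolerability is a stated objective, and the planned size is 27 children per arm, aged from 1 month to just under 4 years. If a child's laboratory values are correlated over the study, the by-visit intervals are wider than they need to be. A modest mean shift in ANC, hemoglobin, ALT or creatinine is then easier to miss. An imbalance already present at Day 1 by chance also feeds into every later contrast.

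**Working it through.** **The plan's own figure.** The documents state no power or detectable difference for laboratory values. The sample size statement (SAP 5) concerns hearing and is used here only for the 27 per arm. It reproduces closely: the effective number of ears is 27 × 2 / (1 + 0.55) = 34.8 per arm. For 40% against 8%, the pooled normal formula at one-sided 2.5% gives 89.6% power, against the stated 90%.

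**Assumptions for the laboratory contrast (none is in the documents).** Total SD 1 at each visit; correlation rho between Day 1 and a later visit; true shift 0.6 SD; two-sided 5%; 27 dosed children per arm; visit treated as a category; complete data.

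**Formulas.** The standard error (SE) of the arm difference at a post-dose visit is:

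- By-visit contrast, as planned: √(2/27) = 0.272, whatever rho is.
- Therapy-by-time contrast (change from Day 1): √[2(1 − rho)] × 0.272.
- Baseline-adjusted (common Day 1 mean, or Day 1 as covariate): √(1 − rho²) × 0.272.

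Power = Φ(0.6/SE − 1.96). For the planned contrast: 0.6/0.272 − 1.96 ≈ 0.24, giving 60%. For baseline adjustment at rho 0.6: SE = √0.64 × 0.272 = 0.218, and 0.6/0.218 − 1.96 ≈ 0.80, giving 79%.

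| rho | By-visit: SE, power | Change from Day 1: SE, power | Baseline-adjusted: SE, power |
|---|---|---|---|
| 0.3 | 0.272, 60% | 0.322, 46% | 0.260, 64% |
| 0.5 | 0.272, 60% | 0.272, 60% | 0.236, 72% |
| 0.6 | 0.272, 60% | 0.243, 69% | 0.218, 79% |
| 0.7 | 0.272, 60% | 0.211, 81% | 0.194, 87% |

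The shift detectable with 80% power is 0.76 SD as planned. With baseline adjustment it is 0.73, 0.66, 0.61 and 0.54 SD at the four values of rho.

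**Does the random intercept already deal with this?** The SAP model was fitted to simulated data: 54 children, five visits, 150 data sets at each of rho 0.3 and 0.6. The by-visit contrast equalled the raw difference in arm means to within 10⁻¹⁴. Its average SE was 0.270 and 0.272. The random intercept therefore takes between-child variance out of the residual but not out of this contrast. Simulated power was 57% and 55% for the planned contrast, 39% and 64% for the interaction, and 61% and 75% with a common Day 1 mean. With 150 data sets each figure has a Monte Carlo SE of about √(0.6 × 0.4/150) = 4 points, so these agree with the formulas. With missing visits the equality to raw means is only approximate.

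**The case against.** Treating baseline as a response in a longitudinal model is valid and common. The within-child comparison is also in the fitted model: the therapy-by-time term contrasts changes from Day 1. Against that term the gain from adjustment is smaller, at 12, 10 and 6 points for rho 0.5, 0.6 and 0.7. This is fair, but SAP 9.5 does not name the interaction as the test. That contrast is also less precise than adjustment at every rho in the table, and worse than the raw contrast below rho 0.5.

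The size depends on an unstated correlation, and one rho need not fit ANC, hemoglobin, ALT and creatinine alike. At rho 0.3 the gain is only 4 points. That stands.

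Some stronger inferences are tempting, and the documents do not support them:

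- **That this is the only formal laboratory comparison.** SAP 9 also plans Wilcoxon rank sum tests for continuous safety parameters and Fisher's exact tests for proportions. As written, they do not use Day 1 either, so they do not repair the loss.
- **That the contrasts are biased.** Under randomization they are not. Day 1 is itself a modelled visit, so a pre-dose imbalance would be visible.
- **That a chance Day 1 gap has an SD of √(2/27) = 0.27.** This assumes simple randomization. The plan states "Study subjects will be stratified according to age at randomization", which limits imbalance linked to age. The documents also give no figure for how strongly these values vary with age.
- **That important marrow toxicity would be missed.** The neutropenia halting rule (Protocol 9.6.2, SAP 6.5.2), the neutropenia incidence in SAP 9 and the lowest-ANC grades in Table 12 do not depend on this model.

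**Conclusion.** The point holds as a minor one. The planned by-visit laboratory contrasts leave between-child variance in their standard error and carry chance Day 1 differences forward, although a pre-dose value is collected. For a 0.6 SD shift with 27 per arm, baseline adjustment raises power from 60% to between 64% and 87% as rho goes from 0.3 to 0.7. Equivalently, it multiplies the contrast variance by 1 − rho², from 0.91 down to 0.51. These figures rest on an assumed correlation, an assumed effect and complete data. What is lost is efficiency in a supportive safety analysis. Validity, the primary endpoint and the halting rule are untouched.

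**What to change.** In SAP 9.5 and the entries for Tables 11a and 11b, choose one of two equivalent routes. Either keep Day 1 in the outcome but constrain the arms to a common Day 1 mean, with arm effects only at post-dose visits. Or model only the post-dose visits and enter the child's Day 1 value as a covariate. State that visit is categorical, and report the adjusted arm difference with a 95% confidence interval at Days 14, 28, 42 and 70.

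The cost is a sentence or two in the SAP, before unmasking. The same mixed-model procedure serves, and no new data are needed, because Day 1 labs are already required before dosing. The common-mean route also keeps any child whose Day 1 value is missing.

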### **6.3.1. Neutropenia**

If the ANC reproducibly (within one week) decreases to  $\leq 500$  cells/mm^3, study drug will be held until the ANC recovers to  $> 750$  cells/mm^3, and then administration of the drug will resume at the normal dose. If the ANC again reproducibly (within one week) decreases to  $\leq 750$  cells/mm^3, the study drug dosage will be reduced by 50% and maintained there as long as the ANC remains  $> 500$  cells/mm^3. If the ANC reproducibly (within one week) decreases to  $\leq 500$  cells/mm^3 on the 50% dosage, then the study medication will be discontinued. In cases of drug interruption, treatment will not be prolonged beyond the originally scheduled 6 week treatment timeframe.

Administration of granulocyte colony stimulating factor (GCSF) is allowed. All administered GCSF doses will be recorded on the concomitant medication sheet. The decision to utilize GCSF is left to the medical discretion of the participating investigator. The parameters for dose adjustment stated above, based upon ANC, will remain in effect even if the patient is receiving GCSF.

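### The by-visit mean ANC and WBC comparison has no rule for values taken after G-CSF, so it leans toward showing no drug effect

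*SAP*

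**What the plan says.** Protocol 6.3.1, in the neutropenia rules: "Administration of granulocyte colony stimulating factor (GCSF) is allowed". No ANC threshold is set: "The decision to utilize GCSF is left to the medical discretion of the participating investigator". The data are kept: "All administered GCSF doses will be recorded on the concomitant medication sheet".

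SAP 9.5 names ANC and WBC among its critical safety parameters. It fits a random-intercept mixed model with time, therapy and their interaction, which "will be used to compare the safety parameter at each time point between the treatment groups". The Table 11a entry in SAP section 17 repeats this for everyone who took at least one dose: "General linear mixed model with random intercept was fitted for each parameter". Figures 4a and 4e plot mean WBC and mean ANC over time. SAP 3.3 specifies a log scale for viral load; no log scale is given for ANC or WBC.

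No SAP section excludes, flags or adjusts a count taken after G-CSF. The recorded doses reach only the medication listing in SAP 7.6 and Table 17, which summarises concomitant medications by arm and visit through Day 48.

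Other outputs also bear on neutropenia. Table 12 gives each child's lowest ANC over Days 1-42 by arm, with no formal test. SAP section 9 assesses neutropenia incidence, names Fisher's exact test for proportions and counts the worst adverse-event grade per child. The halting rule (Protocol 9.6.2, SAP 6.5.2) counts children with Grade 3-4 neutropenia.

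**The concern.** G-CSF is given to raise the neutrophil count, and its place in the neutropenia section implies that it goes mainly to children whose count is low or falling. If the drug causes those low counts, the children most affected can enter the active-arm mean with a normal or high value. The bias then runs toward hiding the effect.

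Neutropenia is the toxicity that the protocol singles out (2.3.1, 9.4) and the only one with a halting table. With about 27 children per arm and an apparently untransformed scale, one or two extreme counts can dominate a visit mean. Table 11a and Figure 4e could then disagree with the incidence tables, and nothing planned would explain why.

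**Working it through.** **The plan's own figure.** The only neutropenia figures stated are the halting probabilities P(X ≥ x | n, 0.375). All 51 rows reproduce to three decimals: 27 of 54 gives 0.0410 (stated 0.041) and 13 of 23 gives 0.0496 (stated 0.050). No figure is stated for the ANC model, so everything below rests on assumed ANC values.

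**Break-even.** Suppose the drug lowers mean ANC by D, and a fraction f of active-arm values at a visit is raised by G on average. The difference in means becomes −D + fG, which vanishes at G = D/f and reverses above it. Take D = 1,000 (assumed).

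| f | source | G needed to cancel |
|---|---|---|
| 1/27 | one child | 1,000 × 27 = 27,000 |
| 2/27 | two children | 1,000 × 27/2 = 13,500 |
| 0.095 | 38% neutropenic (Protocol 9.6.2, oral drug), a quarter of them affected | 10,526 |
| 0.19 | the same, half affected | 5,263 |
| 0.38 | the same, all affected | 2,632 |

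Partial masking starts at any fG above zero. Full cancellation needs many affected children or very large rises.

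**Single-visit simulation.** Assumed: 27 per arm, lognormal ANC, means 3,000 (placebo) and 2,000 (active), log SD 0.5, raw-scale t-test. The lowest active value or values are replaced by the reading shown.

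| Children and reading | Mean deficit | Power |
|---|---|---|
| none | 1,000 | 79% |
| one at 5,000 | about 840 | 61% |
| one at 10,000 | about 650 | 19% |
| one at 20,000 | about 290 | about 0% |

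The deficits can be checked by hand. A deficit of 654 at 10,000 implies a replaced value near 10,000 − 27 × 346 = 658. Then (5,000 − 658)/27 = 161 leaves 839, and (20,000 − 658)/27 = 716 leaves 284. With two children at 20,000 the active mean exceeds placebo in 87-89% of runs. On the log scale, power with one child at 10,000 is about 53% rather than 19%, so the log scale helps but does not remove the bias.

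**Three-visit simulation.** Assumed: placebo median 3,000, drug halves ANC, G-CSF affects the visit after an ANC below 750, t-test at Day 42.

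| G-CSF use and rise | Day 42 difference | Detection | Sign reversed |
|---|---|---|---|
| none | about −1,800 | about 96% | about 0% |
| 50%, 6-fold | −1,374 | 64% | 2% |
| 100%, 10-fold | −224 | 12% | 38% |

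The share of active-arm children with lowest ANC below 750 stays at about 29% throughout. That is by construction: here G-CSF always follows a recorded low value. It would not hold for G-CSF given earlier.

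Both simulations use t-tests, not the planned model. With complete data and visit as a category, the model's by-visit contrast is the difference in visit means, so the shift in the estimate carries over; the power figures are indicative only.

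**Strength of the incidence comparison.** Power of Fisher's exact test at 27 per arm is 84% for 63% v 21%, 80% for 38% v an assumed 5%, and 19% for 38% v 21%. The 63%, 38% and 21% rates come from the earlier studies described in Protocol 2.1.2.1 and 9.6.2.

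**The case against.** A reader might infer that the drug's main harm could look absent or reversed in the trial as a whole. The documents do not support that. A low count recorded before G-CSF stays in Table 12, in neutropenia incidence, in the worst-grade tables and in the halting count. Table 11a also gives 10th and 90th percentiles, and Figure 4f gives ANC boxplots. G-CSF use by arm might be read from Table 17, which runs past the last dose on Day 42.

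Nor is the distortion confined to the active arm. Protocol 2.1.2.1 reports Grade 3-4 neutropenia in 9 of 43 untreated infants (21%), Protocol 6.3 notes that CMV itself can mimic the toxicity, and investigators are masked.

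The large power losses come from extreme values in a raw-scale t-test. A rank test, which SAP section 9 names for continuous safety parameters, keeps about 64% power with one child at 10,000 or 20,000. SAP 9.5, however, specifies the mixed model.

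Comparing ANC as actually managed is also a legitimate summary; dose holds and reductions under Protocol 6.3.1 raise later counts too. Dropping post-G-CSF values as the main analysis has its own bias: removing the lowest 1, 2 or 4 active values shrinks the deficit of 1,000 to about 945, 909 or 805. Carrying a low value forward can overstate how long it lasts.

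All of this stands, and it limits the point to the by-visit means. It does not supply the missing rule. Nor does it recover a child given G-CSF before Grade 3, whom every Grade 3-4 count would miss. How often that would happen is not given.

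**Conclusion.** The concern holds for one set of outputs: the by-visit ANC and WBC comparison in SAP 9.5, Table 11a and Figures 4a and 4e. That these include post-G-CSF counts is read from the SAP's silence, but it is the natural reading. The bias is toward no drug effect, provided G-CSF goes mainly to children with low counts. Its size cannot be fixed from the documents. On the assumptions above it runs from modest (one child at 5,000) to near-complete loss of power (one at 20,000), with reversal only under heavy use or very high counts. The other neutropenia outputs are largely protected, with two limits: early G-CSF escapes them, and the incidence test is weak if the true rates are close. This is a worthwhile, inexpensive improvement, not a threat to the trial's overall safety conclusions.

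**What to change.** In SAP 9.5 and Table 11a:

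- Analyse ANC and WBC on the log scale.
- Keep the all-values model, and state that it describes counts as managed, including G-CSF and dose holds.
- Add a pre-specified sensitivity analysis for values after a child's first G-CSF dose. Either set them to missing in the mixed model or carry forward the last pre-G-CSF value. State the choice and its limits: the first relies on earlier counts to predict the missing ones, and the second can overstate persistence.

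Beside Table 12, report by arm the number of children given G-CSF and the per-child composite of Grade 3-4 neutropenia or G-CSF use, compared by Fisher's exact test.

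The cost is a few lines of SAP text, one merge with the concomitant-medication data and a little more analysis. The data are already collected, and no change to clinical management is proposed.
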